1.2.3. Safety Endpoints

- Incidence and severity of treatment-emergent adverse events (TEAE) (including hypotension and orthostatic hypotension), use of concomitant medications, laboratory assessments, ECG, and vital signs

1.2.4. Exploratory Endpoint

- Change of the weekly average of at-home BP from Baseline to each scheduled, post-baseline visit
- Change and percent change of angiotensin II, renin (Plasma renin activity [PRA]; active renin mass concentration [ARC]), and plasma aldosterone from Baseline to each scheduled, post-baseline visit
- Percentage of subjects reaching the goals of in-clinic SBP \leq 140 mmHg, DBP \leq 90 mmHg, and both over time
- Percentage of subjects and time to requiring antihypertensive therapy during the study
- Assessments of urinary analytes (e.g., cortisol, aldosterone, angiotensin II, albumin, creatinine, protein and sodium) from Baseline to each scheduled, post-baseline visit may be performed
- PK parameters including but not limited to C_{max} (maximum observed ISIS 757456 plasma concentration), T_{max} (time to maximal plasma concentration) and AUC (area under the plasma concentration time profile for ISIS 757456)
- Potential exposure-response analysis using relevant exposure parameters and biomarkers including, but not limited to C_{trough} and plasma AGT may be performed

2. BACKGROUND AND RATIONALE

2.1. Overview of Disease

Resistant hypertension (RHTN) is defined as failure to achieve blood pressure (BP) goal of $< 140/90$ in patients adherent to adequate doses of ≥ 3 medications (1 of which is diuretic) (Judd and Calhoun 2014). Some patients have pseudo-resistance hypertension (HTN) and they are not compliant with their medications or they have white coat HTN.

In US alone, 70 million adults have HTN, of which 12-15% have RHTN. Among these patients 33% of them have uncontrolled RHTN (Judd and Calhoun 2014). In an analysis of National Health and Nutrition Examination Survey database, these patients are more likely to be black, with diabetes, with chronic kidney disease (CKD) Stage 3, with proteinuria and congestive heart failure compared to patients with HTN and without resistant HTN.

2.2. Therapeutic Rationale

Renin-angiotensin-aldosterone system (RAAS) inhibition is well established as a mode of improving HTN (Te Riet et al. 2015) and complications of HTN. While ACEi, angiotensin receptor blockers (ARB) and renin inhibitors are widely used, escape mechanisms are common and lead to incomplete RAAS blockade. Efforts to provide better RAAS blockade using 2 or more agents in this pathway have been complicated by hyperkalemia, hypotension, and acute renal failure (ARF). The effect of this ASO occurs upstream of all the known targets for RAAS inhibitors used in clinical practice, and therefore will potentially reduce escape mechanisms. The hyperkalemia and ARF of RAAS blockade could be secondary to renal specific reduction of

[figure not shown]
these pathways. The *N*-acetyl galactosamine (GalNAc) ASOs have more prominent effect in the liver. As such, the renal sparing effects of this ASO may result in an improved therapeutic index compared with RAAS inhibitors, especially important in subjects with CKD and/or those at submaximal RAAS blockage.

[figure not shown]
[REDACTED]

2.3. ISIS 757456

[REDACTED]

[REDACTED]

[figure not shown]

2.5. Benefit-Risk Assessment

2.5.1. Benefit Assessment

While this compound has been administered to healthy volunteers, it has not been administered to subjects with HTN. Based on its MOA of blocking the RAAS pathway it is expected to lower the BP in subjects with HTN. While there are other compounds (ACEi, ARB, aldosterone blockers, renin inhibitors) that block different components of this pathway, this compound blocks AGT, the most upstream factor in the pathway.

3. EXPERIMENTAL PLAN

3.1. Study Design

This will be a Phase 2, double-blind, randomized, placebo-controlled study of ISIS 757456 conducted in mild hypertensive subjects on an ACEi/ARB and an additional hypertensive medication (see Section 5.1 Inclusion Criteria). Subjects will be stratified based on a screening plasma AGT concentration ($\leq 30 \mu\text{g/mL}$ vs. $> 30 \mu\text{g/mL}$) and randomized in a 2:1 ratio to receive a once-weekly SC treatment and an additional loading dose on Study Day 3 with either ISIS 757456 80 mg or placebo for 6 weeks (See [Study Design and Treatment Schema](#)).

All subjects will complete a 13-week Post-Treatment Period. In the Post-Treatment Period, should a subject's sitting BP on home monitoring exceed 140 mmHg systolic or 100 mmHg diastolic on 2 consecutive days (confirmed by triplicate measurement at the Study Center), the subject's initial HTN medication(s) may be added back per Investigator and Sponsor Medical Monitor judgment and the subject will continue to be followed per protocol in the study.

Refer to Section 8.1 for additional details.

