6.1.1.3. At Home Blood Pressure and Heart Rate Monitoring

Subjects will be provided with a study BPM kit. Subjects will be required to measure their BP and HR at approximately the same time in the morning 3 times a week throughout the study (up to 1 missed BP and HR every 7 days is allowed). Three (3) at home BP and HR measurements should be taken every 7 calendar days on non-sequential days no more than 2 calendar days apart (e.g., Monday, Thursday, Saturday). During the assessments, subjects will first rest in a quiet setting for 5 minutes and then evaluate BP and HR in triplicate each time, with 60 seconds between each measurement and then record the average value. All subjects will be trained by the clinic staff and provided written instructions on how to use the BPM kit. Subjects will contact the Investigator if BP results meet the criteria as outlined in the Safety Monitoring Rules for Blood Pressure and Stopping Rules for Blood Pressure outlined in Section 8.

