2. Prior to Study Day 64 in the Post-Treatment Period or in the Washout Period, should a subject's BPM exceed 170 mmHg (systolic) or 110 mmHg (diastolic) a second measurement must be done within a 30-minute period. If the subject's BP is $>$ 170 mmHg (systolic) or $>$ 110 mmHg (diastolic) within the 30-minute period, an additional BP measurement should be taken within 48 hours at the Study Center, regardless of whether the initial BP measurements were taken in clinic or at home. If the subject then experiences an additional BP measurement $>$ 170 mmHg (systolic) or $>$ 110 mmHg (diastolic) (confirmed by triplicate measurement at the Study Center), they will then be withdrawn from further blinded, randomized treatment. The subject's pre-study antihypertensive medication(s) may be added back per Investigator and Sponsor Medical Monitor judgement. The subject will continue to be followed per protocol in the study. Follow-up for subjects that screen fail due to blood pressure inclusion criteria (see Section 5.1) will not be necessary.
3. On or after Study Day 64 in the Post-Treatment Period, should a subject's BPM exceed 140 mmHg (systolic) or 90 mmHg (diastolic) a second measurement must be done within a 30-minute period. If the subject's BP is $>$ 140 mmHg (systolic) or $>$ 90 mmHg (diastolic) within the 30-minute period, an additional BP measurement should be taken within 48 hours at the Study Center, regardless of whether the initial BP measurements were taken in clinic or at home. If the subject then experiences an additional BP measurement $>$ 140 mmHg (systolic) or $>$ 90 mmHg (diastolic) (confirmed by triplicate measurement at the Study Center), the subject's pre-study antihypertensive medication(s) may be added back per Investigator and Sponsor Medical Monitor judgement. The subject will continue to be followed per protocol in the study.

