8.10.1.1. Allowed Concomitant Therapy

Any other medications deemed necessary by the Investigator are allowed except those listed in the disallowed concomitant therapy.

If the criteria in Section [8.5.3](#) (blood pressure monitoring rules) are met and the patient is in the Post-Treatment Period, antihypertensive agents may be added for BP control in consultation with the Investigator and Sponsor Monitor or designee.

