8.10.1.2. Disallowed Concomitant Therapy

The following are disallowed concomitant therapies:

- Medications for the treatment of HTN (e.g., clonidine, guanfacine, guanabenz, alpha-methyldopa, hydralazine, minoxidil, diazoxide, renin inhibitors) (unless required for safety reasons to control BP in the Post-Treatment Period)
- Medications that may also cause hyperkalemia (e.g., cyclosporine or tacrolimus, pentamidine, trimethoprim-sulfamethoxazole, all heparins)

- Oral or subcutaneous anticoagulants (e.g., warfarin, rivaroxaban, apixaban, lovenox, heparin). Organic nitrate preparations (e.g., nitroglycerin, isosorbide mononitrate, isosorbide dinitrate, or pentaerythritol)
- Sildenafil, tadalafil, vardenafil

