1.1 Study Overview

This will be a Phase 2, double-blind, randomized, placebo-controlled study of ISIS 757456 conducted in mild hypertensive subjects on an ACEi/ARB and an additional hypertensive medication. Subjects will be stratified based on a screening plasma AGT concentration ($\leq 30 \mu\text{g/mL}$ vs. $> 30 \mu\text{g/mL}$) and randomized in a 2:1 ratio to receive a once-weekly subcutaneous (SC) treatment and an additional loading dose on Study Day 3 with either ISIS 757456 80 mg or placebo for 6 weeks.

[figure not shown]
All subjects will complete a 13-week Post-Treatment Period. In the Post-Treatment Period, should a subject's sitting BP on home monitoring exceed 140 mmHg systolic or 100 mmHg diastolic on 2 consecutive days (confirmed by triplicate measurement at the Study Center), the subject's initial hypertension (HTN) medication(s) may be added back per Investigator and Sponsor Medical Monitor judgment and the subject will continue to be followed per protocol in the study.

[REDACTED] All Study Drug injections will be SC administered in the clinic.

This study will be conducted at multiple centers in the United States. Approximately 30 subjects are planned to be enrolled in this study.

The study will consist of screen, run-in, washout (WO), treatment, and post-treatment. The overall length of a subject's participation will be approximately 25 weeks (up to 3 weeks for screening, 1-week run-in, 2 weeks for WO, a 6-week Treatment Period, and 13 weeks of Post-Treatment Evaluation Period).

The study design and treatment schema are depicted as follows:

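### Protocol 3.1 and SAP 1.1 give a different blood-pressure trigger for restarting antihypertensives after treatment from the one in Protocol 8.5.3

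*Combined protocol and SAP*

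**What the plan says.** Protocol 3.1 (Study Design) describes the Post-Treatment Period and allows the initial antihypertensives to be restarted if sitting home readings "exceed 140 mmHg systolic or 100 mmHg diastolic on 2 consecutive days (confirmed by triplicate measurement at the Study Center". SAP 1.1 (Study Overview) gives the same limits: "exceed 140 mmHg systolic or 100 mmHg diastolic on 2 consecutive days". Neither text distinguishes between parts of the period.

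Protocol 8.5.3 (Safety Monitoring Rules for Blood Pressure) splits the period at Day 64. Item 2 covers the time before Day 64 and applies if readings "exceed 170 mmHg (systolic) or 110 mmHg (diastolic) a second measurement must be done within a 30-minute period". Item 3 begins "On or after Study Day 64 in the Post-Treatment Period" and applies if readings "exceed 140 mmHg (systolic) or 90 mmHg (diastolic) a second measurement must be done within a 30-minute period". Both items then require a Study Center measurement within 48 hours, whether the first readings were taken at home or in clinic.

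All of these texts leave the restart to the Investigator and the Sponsor Medical Monitor. Protocol 8.10.1.1 links it to 8.5.3: if those criteria "are met and the patient is in the Post-Treatment Period, antihypertensive agents may be added for BP control". Protocol 8.10.1.2 separately exempts antihypertensives from the disallowed list "unless required for safety reasons to control BP in the Post-Treatment Period", without a number.

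Protocol 6.1.1.3 tells subjects to contact the Investigator when the Section 8 criteria are met, and SAP 2.4.1 refers to protocol 8.5. Protocol 3.1 points only to 8.1, which covers study drug administration and holds no blood-pressure rule.

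**The concern.** Two current texts give different triggers for the same action in hypertensive subjects who are off their medication. They differ in limits, study days, source of the reading and confirmation sequence, so 3.1 cannot be read as a summary of 8.5.3. A site working from 3.1 and a site working from 8.5.3 could act on different readings. Before Day 64, a home reading that meets only the 3.1 trigger carries no contact instruction, because 6.1.1.3 uses the Section 8 criteria.

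The timing of a restart also feeds the analysis. SAP 3.5.2 removes in-clinic systolic and diastolic values after the first antihypertensive, and in-clinic systolic pressure at each visit is a secondary endpoint. SAP 3.5.3 applies the same removal to home blood pressure and the goal-attainment analyses. The percentage of subjects needing antihypertensives, and the time to that need, are exploratory endpoints.

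**Working it through.** The plan states no figure to reproduce. The check sets the rules side by side and counts days and visits.

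**1. The rules**

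| | Protocol 3.1 and SAP 1.1 | Protocol 8.5.3, before Day 64 | Protocol 8.5.3, from Day 64 |
|---|---|---|---|
| Systolic, mmHg | >140 | >170 | >140 |
| Diastolic, mmHg | >100 | >110 | >90 |
| Reading | home | home or clinic | home or clinic |
| Confirmation | 2 consecutive days, then Study Center triplicate | repeat within 30 minutes, Study Center within 48 hours | repeat within 30 minutes, Study Center within 48 hours |

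**2. Where they disagree**

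- Before Day 64 the 3.1 limits are lower by 170 − 140 = 30 mmHg systolic and 110 − 100 = 10 mmHg diastolic. Any pair of readings above an 8.5.3 limit is also above a 3.1 limit. The disputed pairs have systolic ≤170 and diastolic ≤110, with systolic >140 or diastolic >100.
- From Day 64 the systolic limits agree and the 3.1 diastolic limit is higher by 100 − 90 = 10 mmHg. The disputed pairs have systolic ≤140 and diastolic >90 to 100, and only 8.5.3 is met.

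**3. Relevance to the enrolled population**

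Inclusion criterion 11 requires an off-medication systolic pressure above 140 and up to 165 mmHg on Day −7. All of that range is above the 3.1 systolic limit, and none of it is above the 8.5.3 systolic limit before Day 64. With diastolic ≤110, a subject who returns to entry systolic pressure is in the disputed band.

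**4. Earliest trigger dates**

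The Synopsis puts Post-Treatment at Weeks 7 to 19. Week 7 starts on Day 6 × 7 + 1 = 43, and 19 − 7 + 1 = 13 weeks matches the stated length. Take a completer with systolic >140 to 170 and diastolic ≤110 from Day 43:

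- 3.1, two adjacent calendar days: 43 + 1 = Day 44.
- 3.1, two successive home measurement days: 43 + 2 = Day 45, or 43 + 3 = Day 46 (Monday to Thursday in the protocol's example).
- 8.5.3: Day 64, when the 140 mmHg limit begins.

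The differences are 64 − 44 = 20, 64 − 45 = 19 and 64 − 46 = 18 days. They shrink if the first high reading comes after Day 43.

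**5. Visits at stake**

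Appendix A has clinic vital signs after Day 1 on Days 3, 8, 15, 22, 29, 36, 43, 50, 64, 78, 106 and 127, which is 12 visits.

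- Systolic route: a restart soon after Day 44 to 46 removes Days 50, 64, 78, 106 and 127. A restart after a Day 64 trigger removes Days 78, 106 and 127. The difference is Days 50 and 64, or 2 of 12.
- Diastolic-only band from Day 64: a trigger exists only under 8.5.3, so Days 78, 106 and 127 are at stake, or 3 of 12.

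**6. Fit with the home schedule**

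Protocol 6.1.1.3 says home readings "should be taken every 7 calendar days on non-sequential days no more than 2 calendar days apart (e.g., Monday, Thursday, Saturday". If two consecutive days means calendar days, scheduled readings alone can never satisfy 3.1; an extra, unscheduled reading would be needed.

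**The case against.** The strongest reply is that the documents already lead to one place. Protocol 8.10.1.1, 6.1.1.3 and SAP 2.4.1 all point to Section 8, while 3.1 and SAP 1.1 are overviews. Restarting is discretionary under every text, 8.10.1.2 allows it for safety without a number, and under 6.1.5 the Medical Monitor or designee reviews home and clinic readings throughout. This limits the practical effect, and it is why one can say only that sites could differ. But a reader has to infer precedence, and neither discretion nor ongoing review reconciles two stated triggers or supplies a contact instruction.

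The day and visit counts can also be challenged:

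- They are earliest-possible values and leave out the time to Study Center confirmation. If 3.1 were confirmed at the scheduled Day 50 visit, the Day 50 value would precede the restart and only Day 64 would be lost (1 of 12).
- Protocol 6.1.1.3 allows one missed home reading per 7 days, which would shorten the gap further.
- Protocol 6.1.5 speaks of the time after the last dose on Day 36. If the period began on Day 37, the calendar-day trigger could be met on Day 38, a gap of 64 − 38 = 26 days. Day 43 would also be at stake, and a restart before Day 43 would remove the subject from the Per Protocol Set. The Synopsis and the Appendix A layout support the Day 43 start used here.

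Finally, the SAP removes values by actual first administration, identified by medical review at database lock. The analysis rule is therefore well defined under either trigger. That stands.

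**Conclusion.** The contradiction is real and lies wholly in current text. It runs in opposite directions on either side of Day 64, so neither text is uniformly the stricter. For one subject the most it can do is the 20-day and 2-of-12 difference on the systolic route, or the 3-of-12 difference in the diastolic-only band. Both counts assume a completer, a Post-Treatment Period starting on Day 43 and prompt confirmation and restart.

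The documents give no Post-Treatment blood-pressure distribution and no restart rate, so neither the number of subjects affected nor any bias can be calculated. The conflict can shift the rescue endpoints and the later in-clinic blood-pressure data. The primary Day 43 angiotensinogen comparison is essentially unaffected, because the Per Protocol restriction on antihypertensives ends at Day 43. The point should be fixed chiefly because these are safety thresholds.

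**What to change.** Reconcile Protocol 3.1 and SAP 1.1 with Protocol 8.5.3 and 8.10.1.1, so that one set of limits, one confirmation sequence and one set of study days applies. State the rule once and add a cross-reference to it in 3.1 and in SAP 1.1; the existing pointer to 8.1 for dosing in 3.1 can stay. Word any home-based condition so that it can be met on the schedule in 6.1.1.3. Which limits apply is for the sponsor's clinical team to decide.

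The cost is one corrected sentence and one cross-reference in each of the two sections, plus a site memo or short amendment. No analysis method changes.

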3.2. Number of Study Centers

This study will be conducted at multiple centers in the United States.

3.3. Number of Subjects

Approximately 30 subjects are planned to be enrolled in this study.

The 80 mg once-weekly dose is designed to assess the safety, tolerability, and efficacy of Study Drug (ISIS 757456 or placebo) given over a 6-week period. An additional loading dose will be given on Study Day 3. The sample size was selected to ensure that the safety and tolerability of ISIS 757456 will be adequately assessed while minimizing unnecessary subject exposure.

3.4. Overall Study Duration and Follow-up

The study will consist of screen, run-in, WO, treatment, and post-treatment. Please refer to the Schedule of Procedures in [Appendix A](#).

The overall length of a subject's participation will be approximately 25 weeks (up to 3 weeks for screening, 1-week run-in, 2 weeks for WO, a 6-week Treatment Period, and 13 weeks of Post-Treatment Evaluation Period).

Subjects may be required to attend additional visits for monitoring of adverse events (AE) or abnormal investigation results. The frequency of additional monitoring will be determined by the Study Medical Monitor in consultation with the Investigator.

3.4.1. Screening and Run-In

Subject eligibility for the study will be determined within 4 weeks prior to study entry, consisting of up to 3-week screening (Week -6 to Week -4) and a 1-week Run-In Period (Week -3).

During the 1-week Run-In Period the subjects will have home-based blood pressure monitoring (BPM) and an in-clinic visit for vital signs, including BPM. Compliance with antihypertensive medications will be assessed.

3.4.2. Washout

After this 1-week run-in, the subject will withdraw from all of their antihypertensive medications. Antihypertensive medications should be washed out for a period of 2 weeks prior to dosing on Study Day 1.

3.4.3. Treatment

Eligible subjects will be stratified based on a screening plasma AGT concentration (≤ 30 $\mu\text{g/mL}$ vs. > 30 $\mu\text{g/mL}$) and randomized 2 active:1 placebo. Subjects will receive a total of 7 SC doses of Study Drug once-weekly for 6 weeks (Study Days 1, 8, 15, 22, 29, and 36) and an additional loading dose on Study Day 3.

3.4.4. Post-Treatment

Subjects are to return to the Study Center for follow-up visits on Study Days 43, 50, 64, 78, 106 and 127. The final study visit will be Study Day 127 (Week 19).

3.5. End-of-Study

The End-of-Study is defined as the date of the last visit of the last subject.

4. SUBJECT ENROLLMENT

4.1. Screening

Before subjects may be enrolled into the study, the Sponsor requires a copy of the Study Center's written institutional review board (IRB) approval of the protocol, informed consent form, and all other subject information and/or recruitment material.

Subjects must sign the consent form before any screening tests or assessments are performed. At the time of consent, the subject will be considered enrolled into the study and will be assigned a unique screening number before any study procedures, including screening procedures, are performed. At the time of randomization, subjects will be assigned a unique subject identification number. This number will be used to identify the subject throughout the trial and must be used on all study documentation related to that subject. The screening number and subject identification number must remain constant throughout the entire trial. Screening numbers and subject identification numbers, once assigned, will not be re-used.

4.2. Randomization

Subjects will be randomized after all screening, run-in, and WO assessments through Study Day -7 have been completed and after the Investigator has verified that they are eligible per criteria in Sections 5.1 and 5.2 and after review by Sponsor Medical Monitor or designee. No subject may begin treatment prior to randomization and assignment of a unique subject identification number.

Eligible subjects will be stratified based on a screening plasma AGT concentration screening plasma AGT concentration ($\leq 30 \mu\text{g/mL}$ vs. $> 30 \mu\text{g/mL}$) and then subjects will be randomized 2:1 to receive ISIS 757456 or placebo as outlined in Section 3.1. Eligible subjects must have a plasma AGT concentration $\geq 20 \mu\text{g/mL}$ to participate in the study (see Section 5.1 Inclusion Criteria). The Sponsor or designee will prepare the randomization list and utilize an automated IRT (Interactive Response Technology) system.

